# 6.6 Post Procedure to Discharge

The following assessments will be performed within 12-24 hours post procedure or prior to hospital discharge, whichever occurs first:

- Physical Exam and Vital Signs
- Hemoglobin, hematocrit, and free hemoglobin
- Adverse Events assessment

# 6.7 30 Days Follow-up (± 7 Days)

Subjects will return for a follow-up visit at 30 days and the following assessments will be performed:

- Physical Exam and Vital Signs
- Rutherford Classification
- ABI
- Duplex Ultrasound of treated lesion per Ultra Sound Core Lab protocol
- Angiogram performed only if clinical symptoms requiring intervention during follow-up for TVR or TLR
- VascuQoL Questionnaire
- Adverse Events assessment

# 6.8 6 Months Follow-up (± 14 Days)

Subjects will return for a follow-up visit at 6 months and the following assessments will be performed:

- Physical Exam and Vital Signs
- Rutherford Classification
- ABI
- Duplex Ultrasound of treated lesion per Ultra Sound Core Lab protocol
- Angiogram performed only if clinical symptoms requiring intervention during follow-up for TVR or TLR
- VascuQoL Questionnaire
- Adverse Events assessment

**Table 6-1: Schedule of Events** 

Assessment	Screening / Baseline/Pre- procedure	Procedure	Discharge	30 Days (±7 days)	6 months (±14 days)
Informed Consent	X				
Medical History	X				
Physical Exam	X		X	X	X
Laboratory Assessments	X	X			

Urine Pregnancy Test if female	X				
Rutherford Classification	X			X	X
ABI	X			X	X
VascuQoL Questionnaire	X			X	X
Hemoglobin, hematocrit, and free hemoglobin	X	X	X		
Angiogram	X	X		X a	X a
Duplex Ultrasound	X b			X	X
Medications	X		X	X	X
Adverse Events	X	X	X	X	X

<sup>aAngiograms will be performed at the follow-up visits for verification of restenosis of the treated lesion/vessel site(s) only if the subject has clinical symptoms requiring intervention.

# 6.9 Unplanned Follow-up

Subjects returning for unscheduled visits complaining of new signs and/or symptoms will be documented as an unplanned follow-up and, at the investigators' discretion perform diagnostic evaluations. The reason should be reported as an adverse event if applicable.

# 6.10 Subject Early Discontinuation / Withdrawal and Replacement of Subjects

All subjects are informed of their right to withdraw from the clinical study at any time. Additionally, the investigator may prematurely discontinue any subject's participation in the study if the investigator feels that the subject can no longer fully comply with the requirements of the study or if any of the study procedures are deemed potentially harmful to the subject. However, it is anticipated that such withdrawals will be infrequent to ensure the integrity of the study. The reason for early discontinuation will be documented in the source documents and case report forms.

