# 4.2 Sample Size and Number of Centers

The study may enroll up to 10 subjects and will be conducted at up to 2 investigational sites in the United States.

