#### 5 STUDY ENDPOINTS

# 5.1 Primary Safety Endpoints

The primary safety endpoint is freedom from a composite of new on-set major adverse events (MAE) through 30-day follow-up as adjudicated by an independent clinical adjudicator.

The components of the MAE are defined as:

- Cardiovascular related death: All cardiovascular cause mortality.
- **Myocardial infarction (MI):** Any newly diagnosed MI post procedure, defined as CK-MB ≥2X upper limit normal (ULN).
- Clinically driven target lesion revascularization (TLR): any repeat percutaneous or surgical intervention to treat objectively documented symptoms of recurrent ischemia attributable to the treated lesion.
- Clinically significant target vessel dissection: NHLBI grade C or greater as confirmed by angiography.
- Clinically significant target vessel perforation: NHLBI Type III as confirmed by angiography.
- **Unplanned major target limb amputation:** Amputation of the transmetatarsals or higher that was not previously planned as part of the overall treatment strategy.
- Clinically relevant distal embolization: Emboli requiring surgical or medical intervention and/or the presence of symptoms.
- **Pseudoaneurysm:** disruption of the arterial wall at the treatment site as confirmed by angiography.

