# 6.11 Lost to Follow-up

Every attempt will be made to have all subjects complete the follow-up visit schedule. A subject will not be considered lost to follow-up unless efforts to obtain compliance are unsuccessful. At a minimum, the effort to obtain follow-up information will include three attempts to make contact

b if available

via telephone and if unsuccessful, then a certified letter from the investigator will be sent to the subject's last known address.

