#### 8 STATISTICS

This study is a one or two center, prospective, non-randomized single-arm Early Feasibility Study. All clinical endpoints will be summarized with descriptive statistics without hypothesis testing. For continuous variables, the range (minimum, maximum), mean, standard deviation, median, first and third quartiles (Q1 and Q3) may be reported, while for discrete variables, count and percentage will be provided.

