# 12.9 Protocol Deviations / Violations and Medical Emergencies

A protocol deviation or violation is a failure to comply with the requirements of the clinical study as specified in the protocol. Examples of protocol deviations include late visits, missed visits, required follow-up testing not completed. An example of a major protocol violation includes enrollment of a study subject who fails to meet inclusion/exclusion criteria as specified in the protocol. Each investigator shall conduct this clinical study in accordance with the study protocol and any conditions required by the reviewing IRB.

Deviations/violations from clinical protocol requirements will be reviewed and evaluated on an ongoing basis and, as necessary, appropriate corrective actions put into place. See Table 12-1: Reports Required from Investigators to Sponsor for reporting timelines for emergency deviation.

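### Section 6.10 lets the investigator end a treated subject's participation without separating study tests from outcome follow-up, so late MAEs and 6-month outcomes can be lost informatively

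*Combined protocol and SAP*

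**What the plan says.** Protocol Section 6.10 gives two grounds on which the investigator, rather than the subject, may end participation. The first is that "the investigator may prematurely discontinue any subject's participation in the study if the investigator feels that the subject can no longer fully comply" with what the study requires. The second applies "if any of the study procedures are deemed potentially harmful to the subject". The section adds that "it is anticipated that such withdrawals will be infrequent to ensure the integrity of the study" and asks for the reason to be documented in the source records and CRFs. It sets no exit assessment and no further contact.

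Two other sections deal with incomplete follow-up. Section 6.11 opens with "Every attempt will be made to have all subjects complete the follow-up visit schedule" and requires at least three telephone attempts and then a certified letter before a subject counts as lost. Section 12.9 treats incomplete attendance as a deviation: "Examples of protocol deviations include late visits, missed visits, required follow-up testing not completed".

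The primary safety endpoint in Section 5.1 is "freedom from a composite of new on-set major adverse events (MAE) through 30-day follow-up". Section 5.3 adds related SAEs, TLR/TVR, patency, ABI, Rutherford class and VascuQoL at 30 days and 6 months. On size, Section 4.2 says "The study may enroll up to 10 subjects". On analysis, Section 8 says "All clinical endpoints will be summarized with descriptive statistics without hypothesis testing", with counts and percentages for discrete variables. The synopsis names an intent-to-treat population, but neither it nor Section 8 says how a subject with unknown outcome is handled.

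**The concern.** The investigational treatment is given once, at the index procedure. After that day no study treatment is left to stop. Sections 6.7 and 6.8 leave only examination, Rutherford class, ABI, duplex, a questionnaire and AE assessment, with angiography only when symptoms call for intervention. A test that a subject cannot undergo, or that causes worry, could be left out while the subject stays under observation. Section 6.10 does not offer that middle course. What it allows to end is participation in the study as a whole.

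The two grounds are also not neutral with respect to outcome. A subject who cannot keep up with visits, or for whom a study test is thought harmful, is plausibly a subject who is deteriorating. If such subjects leave before day 30 or month 6, the remaining data describe a healthier group than the one treated. In a first-in-human study with a safety proportion as its primary result, that bias favours the device.

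**Working it through.** **Figure to reproduce.** None. The plan states no power, margin, dropout rate or expected MAE rate. The check is therefore a reading of the safeguards, followed by a sensitivity calculation under stated assumptions.

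**Step 1. Does another provision recover the outcome after an investigator discontinuation?**

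| Provision | What it covers | What it leaves open |
|---|---|---|
| Section 11 | All AEs recorded; assessed at the procedure and at study follow-up visits | A discontinued subject has no further visits |
| Section 11.4 | AEs ongoing at first report are followed until resolved or stable | New events after exit |
| Section 11.7 | Deaths during the study are reported | Whether this reaches a discontinued subject is not stated |
| Section 6.11 | General retention aim; calls and letter before a subject is declared lost | Contact steps are written for subjects at risk of being lost, not for those the investigator removes |
| Section 12.2 | Adjudication of events raised by the investigator or sponsor | Events nobody has ascertained |
| Synopsis and Section 8 | ITT population; descriptive summaries | No missing-outcome or denominator rule |

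None of these requires new day-30 or 6-month outcome information in a discontinued subject.

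**Step 2. Which endpoints are exposed?** Technical success (5.2) is determined immediately after treatment. Section 6.5.1 requires angiography after atherectomy, after any adjunctive intervention and at the end of the procedure, so dissection, perforation and other MAEs seen then are already known. The exposed MAE components are the later ones: cardiovascular death, MI, TLR, amputation, and late embolization or pseudoaneurysm. All 6-month endpoints are exposed as well.

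**Step 3. How far can the primary safety proportion move?** Let *N* be treated subjects, *w* those discontinued before day 30 with unknown status, and *e* the MAEs observed among the rest.

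- Followed subjects only: (*N* − *w* − *e*)/(*N* − *w*)
- Worst case over all treated: (*N* − *w* − *e*)/*N*
- Best case over all treated: (*N* − *e*)/*N*
- Gap between the bounds: *w*/*N*

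*N* = 10 is the maximum in Section 4.2. The values of *w* and *e* are assumptions.

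| *e* | *w* | Followed only | Worst case | Best case |
|---|---|---|---|---|
| 0 | 1 | 9/9 = 100% | 9/10 = 90% | 10/10 = 100% |
| 0 | 2 | 8/8 = 100% | 8/10 = 80% | 10/10 = 100% |
| 0 | 3 | 7/7 = 100% | 7/10 = 70% | 10/10 = 100% |
| 1 | 1 | 8/9 = 88.9% | 8/10 = 80% | 9/10 = 90% |
| 1 | 2 | 7/8 = 87.5% | 7/10 = 70% | 9/10 = 90% |

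Each unknown subject opens a gap of 1/10 = 10 percentage points, and more if fewer than 10 are treated. With no observed MAE, the followed-only figure stays at 100% however many subjects have left.

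**The case against.** The strongest reply is that the protocol is less bare than Section 6.10 alone suggests. A reader might infer that only the reason is kept once a subject is discontinued. That is true of Section 6.10 but not of the protocol: Sections 11.4 and 11.7 keep ongoing AEs and deaths in view, and Section 6.11 states a retention aim for all subjects. A limb event reported before exit should be followed to its conclusion, including an amputation that grows out of it. This stands, and it narrows the gap to new events after exit.

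A reader might also see a contradiction between 6.10 and Sections 6.11 and 12.9. The documents do not support that. A discretionary power, a retention effort and a definition of deviations can coexist. What is missing is a rule for choosing among them when a subject cannot comply.

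Third, it is tempting to say that the worst-off subjects will be removed, or that a removed subject will be scored MAE-free. The wording permits the first but does not show it, and the protocol expects withdrawals to be rare. No text says the second. Nor does every serious event bear on the composite: stroke, for example, is not an MAE component.

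Finally, this is a descriptive feasibility study of at most 10 subjects. Even complete follow-up with no MAE has an exact 95% interval of 69.2% to 100%, so one unknown subject sits inside wide sampling uncertainty. That is fair, and there is no loss of power or type I error here. But an interval does not correct a directional bias, and the plan specifies no interval.

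**Conclusion.** The concern holds in a limited form. Section 6.10 lets the investigator end a treated subject's whole participation on grounds plausibly linked to poor outcome, and nothing elsewhere secures new day-30 or 6-month outcomes in that subject. The consequence is a possibly biased descriptive rate for later MAEs and for the 6-month endpoints. The primary effectiveness endpoint and procedural MAEs are untouched.

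The size is 10 percentage points of the primary safety result per subject with unknown status, assuming 10 treated. The illustrations (one to three discontinuations before day 30, none or one observed MAE) are assumptions, because the plan gives no rate beyond an expectation that withdrawals are infrequent. That expectation is not a control, and at this sample size one case is enough to change the headline figure. The change should be made, as it is specific and inexpensive.

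The heading of 6.10 also mentions replacement while its text gives no rule. A reader might infer that treated subjects will be replaced, but the documents do not say so. It is a drafting omission and carries no weight here.

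**What to change.** Amend Section 6.10 for the period after device use:

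1. Inability to comply, or concern about a study test, leads to omission of that visit or test, recorded as a deviation under Section 12.9. Outcome follow-up continues unless the subject withdraws consent.
2. At any exit, a final AE/MAE assessment is made and recorded.
3. Where consent allows, MAE, SAE and vital status at day 30 and 6 months are obtained by telephone or from records, using the contact effort in Section 6.11.

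In Section 8, state that all treated subjects stay in the denominator of the MAE-free proportion. A subject with unknown day-30 status is shown once as an event and once as no event, and is never simply counted as MAE-free.

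The cost is protocol wording and a few extra contacts or record checks in at most 10 subjects. The MAE-free figure may turn out less favourable than one based on followed subjects alone.

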# 6.11 Lost to Follow-up

Every attempt will be made to have all subjects complete the follow-up visit schedule. A subject will not be considered lost to follow-up unless efforts to obtain compliance are unsuccessful. At a minimum, the effort to obtain follow-up information will include three attempts to make contact

b if available

via telephone and if unsuccessful, then a certified letter from the investigator will be sent to the subject's last known address.

#### 7 BENEFIT / RISK ANALYSIS

## 7.1 Benefits

Participation in this study is voluntary. There will be no direct benefits of participating in this study. Information gathered from this study will help confirm the safety and efficacy of the device in treating de novo, severely calcified peripheral lesions.

#### 7.2 Risks

The risks of the investigational procedure to subjects is similar to that of other Atherectomy procedures.

Possible risks associated with the Cardio Flow FreedomFlowTM Orbital Atherectomy System that may occur and/or require intervention include, but are not limited to:

- Allergic reaction to medication/media/device components
- Amputation
- Anemia
- Aneurysm
- Bleeding complications which may require transfusion
- Cerebrovascular accident (CVA)
- Death
- Distal embolization
- Device embolization
- Entry site complications including hematoma
- Hemolysis
- Hypotension/hypertension
- Infection
- Myocardial infarction
- Pain
- Pseudoaneurysm
- Restenosis of treated segment that may require revascularization
- Renal insufficiency/failure
- Slow flow or no reflow phenomenon
- Dissection
- Perforation
- Thrombus

- Vessel closure, abrupt
- Vessel injury, including dissection and perforation that may require surgical repair
- Vessel spasm
- Vessel occlusion

# 7.3 Minimization of Risk and Monitoring Procedure

Cardio Flow, Inc. has attempted to mitigate risks as much as possible through product design, testing, and through careful labeling and instructions for use.

#### 8 STATISTICS

This study is a one or two center, prospective, non-randomized single-arm Early Feasibility Study. All clinical endpoints will be summarized with descriptive statistics without hypothesis testing. For continuous variables, the range (minimum, maximum), mean, standard deviation, median, first and third quartiles (Q1 and Q3) may be reported, while for discrete variables, count and percentage will be provided.

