# 5.2 Primary Effectiveness Endpoint

The primary effectiveness endpoint is technical success. The technical success is defined as the ability of the FreedomFlowTM Orbital Atherectomy System to achieve a residual diameter stenosis  $\leq 50\%$  immediately post treatment without adjunctive balloon inflation, as assessed by an independent Angiographic Core Laboratory.

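### The two binary primary endpoints are summarised by count and percentage only, with at most 10 subjects; exact confidence intervals should be added, and the claim that the data will help confirm safety and efficacy softened

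*Combined protocol and SAP*

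**What the plan says.** Section 8 calls the trial a "prospective, non-randomized single-arm Early Feasibility Study" and sets the analysis in two statements. The first is that "All clinical endpoints will be summarized with descriptive statistics without hypothesis testing". The second lists the summaries: location and spread for continuous variables, "while for discrete variables, count and percentage will be provided". No section names a confidence interval, a precision target, a performance goal or an assumed event rate.

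Both primary endpoints fall under the rule for discrete variables. Section 5.1 defines safety as "freedom from a composite of new on-set major adverse events (MAE) through 30-day follow-up". Section 5.2 states: "The primary effectiveness endpoint is technical success", meaning a core-laboratory residual stenosis of no more than 50% after the device alone.

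Section 4.2 gives the size as a cap: "The study may enroll up to 10 subjects". No minimum and no rationale are given. On the use of the results, Section 7.1 says: "Information gathered from this study will help confirm the safety and efficacy of the device".

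**The concern.** With 10 subjects or fewer, sampling uncertainty is large compared with anything the percentages can show. The plan asks for no statement of that uncertainty, yet Section 7.1 presents the data as helping to confirm safety and efficacy.

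The results will also be read outside the sponsor. Table 12-1 sends an interim and a final report to the IRB, and Section 12.12 expects an abstract and a journal paper. A result of 10 (100%) free of MAE could be taken there as evidence of a low event rate. The composite includes cardiovascular death, major amputation and perforation, so it matters which rates a clean result leaves open.

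**Working it through.** **Plan's own figure.** There is nothing to reproduce. The 10 subjects are a cap, with no alpha, power, assumed rate or margin behind it.

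**Inputs.** n ≤ 10 (Section 4.2); two binary primary endpoints (Sections 5.1 and 5.2). The documents give no confidence level, so 95% two-sided exact (Clopper-Pearson) is my assumption. Other conventions are shown below as a range.

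**Zero events.** The exact two-sided 95% upper limit is 1 − 0.025^(1/n).

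| Subjects, all MAE-free | Upper limit for MAE rate | Lower limit for freedom from MAE |
|---|---|---|
| 10 | 1 − 0.025^(1/10) = 30.8% | 69.2% |
| 9 | 1 − 0.025^(1/9) = 33.6% | 66.4% |
| 8 | 1 − 0.025^(1/8) = 36.9% | 63.1% |
| 5 | 1 − 0.025^(1/5) = 52.2% | 47.8% |

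**Other results at n = 10** (exact two-sided 95%, for freedom from MAE or for technical success):
- 9/10: 55.5% to 99.7%
- 8/10: 44.4% to 97.5%

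**Sensitivity to the convention, 0/10 events:**
- exact two-sided 95%: 30.8%
- rule of three: 3/10 = 30.0%
- Wilson two-sided 95%: z²/(n + z²) = 3.84/13.84 = 27.8%
- exact one-sided 95%: 1 − 0.05^(1/10) = 25.9%
- Jeffreys equal-tailed 95%: 21.7%

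The upper limit therefore lies between 21.7% and 30.8%. A true MAE rate of 20% stays inside all of these limits.

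**Chance of a clean result.** P(0 events in 10) = (1 − p)^10:
- p = 10%: 34.9%
- p = 20%: 10.7%
- p = 30%: 2.8%

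**Denominator.** Three sections define enrolment differently: consent plus eligibility (6.2), the same plus treatment with the device (6.3), and angiographic eligibility plus guidewire crossing through the true lumen (6.5.1). The intent-to-treat population is named only in the synopsis and is not defined. Suppose ten subjects are crossed with the wire, nine are treated successfully, and one is never treated with the device. Technical success is 9/10 (lower limit 55.5%) under 6.5.1 if that subject counts as a failure, but 9/9 (lower limit 66.4%) under 6.3.

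**Unit.** Sections 6.1.1 and 6.5.1 allow up to three target lesions per subject, and Section 5.2 does not say whether success is counted by lesion or by subject. Ten subjects could supply 30 lesions. Treating 30/30 as independent would give a lower limit of 0.025^(1/30) = 88.4%, against 69.2% for 10/10 subjects. Lesions in one leg of one subject are not independent, so 88.4% would overstate the precision.

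**The case against.** The strongest reply is that the plan fits its design. This is a small first-in-human feasibility study with no test, comparator, performance goal or go/no-go rule, so no decision in the protocol would change if an interval were added. The governing objective in Section 3 is to evaluate, and the wording about confirming stands in the benefits section and says only that the data will help. Section 8 does not forbid intervals. All of this stands, and it is why the point concerns reporting.

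It does not remove the point. An interval describes precision and needs no hypothesis, so it is compatible with a descriptive plan. With so few subjects it is also the simplest guard against over-reading.

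A reader might infer four stronger things that the documents do not support:
- **That the report would hide the uncertainty.** It would not. The count is given with the percentage, so the denominator is visible and anyone can derive an interval. What is missing is the stated uncertainty.
- **That a 30% MAE rate cannot be excluded after 0/10.** At n = 10 this holds for the exact two-sided 95% limit, and only narrowly: 2.8% against a 2.5% cut-off. The one-sided exact limit (25.9%) and the Wilson limit (27.8%) both exclude 30%.
- **That the sample size is wrong.** A cap of 10 without a power calculation is legitimate for early feasibility.
- **That a later study will be sized from these estimates.** No section says so.

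**Conclusion.** The point holds as a reporting improvement, not as an error in design, sample size or analysis. Section 8 plans no measure of precision for either primary endpoint. The best possible safety result, 0 MAE in 10, leaves an exact two-sided 95% upper limit of 30.8%, or 36.9% if only 8 subjects enrol. Such a result cannot confirm safety, and the Section 7.1 wording claims more than the data can bear. By the same arithmetic, 10/10 technical successes would have a lower limit of 69.2%.

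The figures rest on two assumptions: a two-sided 95% exact interval, which the documents do not specify, and one binary outcome per subject. Other conventions lower the 0/10 limit, to 21.7% at the least, without changing the conclusion. The interval cannot be computed unambiguously until the denominator and the unit for technical success are settled.

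**What to change.** 1. In Section 8, add that freedom from MAE through 30 days and technical success will each be reported with an exact (Clopper-Pearson) two-sided 95% confidence interval at subject level, without hypothesis testing.
2. State one denominator for both. Reconcile the enrolment definitions in Sections 6.2, 6.3 and 6.5.1 with the intent-to-treat population in the synopsis, and define that population in Section 8.
3. State how a subject with two or three treated lesions is classified for technical success. One option is to require every treated target lesion to meet the threshold. Lesion-level counts can be listed as supporting detail.
4. In Section 7.1, replace *help confirm* with *provide initial estimates of*.

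Sample size, conduct and subject burden do not change. The interval itself takes one line of code. The real work is agreeing the denominator and the multi-lesion rule, which should be done before any outcome is seen. The reported results will look less certain.
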